### **6.2 Reporting of Numerical Values**

Raw data will be presented with the exact precision that it was collected on the eCRF or other external data sources.

The number of decimal places to display for calculated data will be determined by the scale of measurement. No decimal places will be displayed if the smallest calculated value is 100; 1 decimal place will be displayed when all calculated values are within the interval (10, 100), with 10 being inclusive; 2 decimal places are displayed when all calculated values are within (1, 10), with 1 being inclusive; 3 decimal places are displayed for calculated values within (0.1, 1), with 0.1 being inclusive; and so on for even smaller scales of measurement.

Percentages will be reported with exactly one decimal place. For summary statistics, means, medians, and confidence intervals will be displayed to one more decimal place than was determined above, dispersion statistics will have 2 more decimal places, and the minimum and maximum will be displayed to the same number of decimal places as determined by the rules above. Blank fields on an eCRF will be displayed as blank fields in corresponding listings.

### 6.3 Handling of Missing Data

Unless otherwise explicitly specified, missing data will not be imputed; observed cases will be used in the analyses.

### 6.4 Statistical Software

Statistical analyses will be performed using SAS version 9.4 or higher.

## 7.0 STATISTICAL METHODS

### 7.1 Sample Size Justification

Based on the results presented in Section 3.4 of CIP for Version 1.3 of the WaveCrest device in the WAVECREST 1 study and during limited market release, a total of 7 (4.2%) subjects out of 165 implanted subjects have experienced an occurrence of the composite safety endpoint of all-cause mortality, pericardial effusion requiring intervention, device embolization from the LAA, device thrombus, or ischemic stroke. If the expected rate of occurrence of the composite safety endpoint is 5%, then a sample size of 56 subjects will result in the upper bound of a two-sided exact 95% confidence interval being less than 15%. Assuming a drop-out rate of ten percent, total enrollment in this study will be at least 63 subjects (56/0.9 rounded up).

### 7.2 Demographics and Baseline Characteristics

A minimum of the following demographic and baseline characteristics will be summarized by each analysis set: age at enrollment, sex, race, ethnicity, weight, height, body mass index, prior cardiovascular history, baseline CHADS2 score, baseline CHA2DS2-VASc score, baseline HAS-BLED score, baseline QVSFS score, modified Rankin Scale score, congestive heart failure, hypertension, diabetes, previous stroke/TIA, NYHA Class, type of atrial fibrillation, time of onset of atrial fibrillation (summarized continuously in years as well as categorically with cut points of < 1 year or ≥ 1 year), left ventricular ejection fraction (LVEF), left atrial appendage anatomy shape and morphology, and use of antiplatelet and anticoagulation medications.

### 7.3 Safety Endpoint

The safety endpoint for the investigation is a composite of the following through 45 days follow-up post implant:

- All-cause mortality
- Pericardial effusion requiring intervention
- Device embolization (major)
- Device thrombus
- Ischemic stroke

All safety events occur within the 45 days follow up visit window (up to Day 60) will be adjudicated by the Sponsor. The safety endpoints analysis will be based on Sponsor Assessment of Adverse Events data. No formal statistical inference will be made. The analysis will be descriptive for the ITT analysis set. The number and percentage of subjects experiencing any occurrence of the composite safety endpoint will be summarized assuming binomial distribution. The exact two-sided 95% confidence intervals will be constructed for the composite endpoint. A similar analytical approach will be performed for each component as well.

#### 7.4 Clinical Performance Endpoints

Descriptive clinical performance endpoints through 45 days (+15 days) follow-up will be summarized and presented as detailed below for both ITT and As-Treated analysis sets. No formal statistical inference will be made and the exact two-sided 95% confidence intervals will be constructed.

- **Device success**

Device success will be calculated as the proportion of subjects who have the device deployed and implanted in the correct position.

- **Technical Success**

The technical success rate will be calculated as the proportion of subjects who experience successful placement and release of the occluder in the LAA with LAA closure (defined as no leak > 5mm on color Doppler TEE) and discharge from the cardiac catheterization laboratory without the occurrence of device-related complications.

- **Procedural success**

The procedural success rate will be calculated as the proportion of subjects who experience successful placement and release of the occluder in the LAA with LAA closure (defined as no leak > 5mm on color Doppler TEE) and discharge from the cardiac catheterization laboratory without device-related complications and without procedure-related complications other than minor device embolization (defined as device embolization that can be resolved by percutaneous technique without surgical intervention or damage to surrounding cardiovascular structures).

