3.4 Clinical Experience with the WaveCrest Device

The WaveCrest device was studied in the Coherex WAVECREST 1 Left Atrial Appendage (LAA) Occlusion Study (WAVECREST 1 Study). One-hundred fifty-five (155) patients were treated with the WaveCrest LAA occlusion device at 19 investigational sites in Europe, Australia and New Zealand. Three device versions were studied: **Version 1.1** (N=9), **Version 1.2** (N=73) (enhancements were made to the device and user training), **Version 1.3** (N=73) (enhancements were made to the anchor frame and delivery catheter). The study enrolled elderly patients with an average CHADS₂ Score of 2.5 and at high risk of stroke. More than half (65%) the patients were contraindicated for anticoagulation. Clinical results on device **Version 1.3**, which is the device which received CE mark are as follows: procedural success was achieved in a majority of patients (96%). Procedure duration averaged 68 minutes, with forty-seven percent (47%) of procedures requiring no device repositioning. On average, 1.3 devices were used (i.e., attempted) per patient. Pericardial effusions/tamponade occurred at a rate of 2.7% with none requiring surgical intervention. No safety-related events occurred after 45 days. At 45 days, LAA closure, defined in the study as residual gap ≤ 3 mm, occurred in 97% of patients. With LAA closure defined as residual gap ≤ 5 mm, LAA closure rate at 45 days was 100%. There were no unanticipated adverse events or unanticipated adverse device effects.

	Title: WAVECREST Post Market Clinical Follow-Up (PMCF) Study	Doc. #: CHX_IP015	Rev: D
---	---	-----------------------------	------------------

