The WaveCrest device received the CE Mark in August 2013 and became available commercially in Europe in October 2013. Procedural success was high during limited market release, with 88/92 (96%) procedural success rate through July 2014. Pericardial effusions occurred at a rate of 3.3% (3/92). There was one device embolization (1.1%). In 2 patients (2.2%), a thrombus was discovered on a follow-up TEE. There were no procedural strokes. In 2 patients, there was damage to the inner liner of the Delivery Sheath. Both cases were considered “incidents” and warranted a Field Safety Notice (FSN) and Field Safety Corrective Action (FSCA) in August 2014, resulting in modification to the Delivery Sheath liner. In addition, some minor enhancements were made to the device. These device enhancements were approved in a Change Notification to the original CE mark.

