3.5 Rationale to Conduct Clinical Study

The WAVECREST PMCF Study is intended to evaluate the safety and performance of Coherex’s WaveCrest LAA Occlusion System in current medical practice through 45 day follow-up following minor system enhancements. Forty-five days is the recommended follow-up period in the IFU and the recommended standard of care in clinical practice for this type of procedure. This timeframe provides an appropriate length of time from the implant procedure to capture any procedural safety-related events based on the canine study and prior clinical studies. Performance of the device is demonstrated by procedural and device success at implant.

The WaveCrest device is passive in nature once it is deployed in the LAA. Initially the anchors hold the device in position, however, tissue in-growth (endothelialization) begins immediately in the occluder material once the device is implanted. Canine testing showed the safety and performance of the device modifications during the implant procedure and complete implant endothelialization by 30 days. The WAVECREST 1 study and the initial limited market release have effectively demonstrated the safety and performance profile during implant and long-term safety of the occluder materials in clinical use .

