5.2 Endpoints

Safety and performance of the WaveCrest device through 45 days follow-up will include the following endpoints:

- Composite rate of:
 - All-cause mortality
 - Pericardial effusion requiring intervention
 - Device embolization (major)
 - Device thrombus
 - Ischemic stroke
- Device Success - Device deployed and implanted in the correct position
- Technical Success at implant
 - Occlusion of the LAA
 - No device-related complications
 - No leak >5mm on color Doppler TEE
- Procedural Success
 - Technical success
 - No procedure-related complications except uncomplicated (minor) device embolization (resolved by percutaneous retrieval during the procedure without surgical intervention or damage to surrounding cardiovascular structures)

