- the event depends on a false result given by the device used for diagnosis, when applicable;
- In order to establish the relatedness, not all the criteria listed above might be met at the same time, depending on the type of device/procedures and the event.

In general, any event that occurs within 30 days is considered related to the procedure, unless clear signs are available that they are not.

The investigator will distinguish between adverse events related to the device and those related to the implant procedure. An adverse event can be related both to the implant procedure and the device. Complications of procedures are considered not related if the said procedures would have been applied to the patients also in the absence of device use/application.

In some particular cases the event may be not adequately assessed because information is insufficient or contradictory and/or the data cannot be verified or supplemented. The investigator will make the maximum effort to define and categorize the event and avoid these situations. Where the investigator remains uncertain about classifying the event, it should not exclude the relatedness and classify the event as “possible”.

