#### 7.5 Other Safety Analysis - Adverse events (AEs)

Site reported adverse events (AEs) during the study will be coded using the Medical Dictionary for Regulatory Activities (MedDRA). The number and percentage of subjects reporting adverse events will be summarized by MedDRA system organ class and preferred term for both ITT and As-Treated analysis sets. Separate summaries will also be provided for device-related AEs and procedure-related AEs. All serious adverse events (SAEs), device-related SAEs, and procedure-related SAEs will also be summarized by system organ class and preferred term. All adverse events occurring through the 45-day (+15 days) follow-up will be summarized.

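### SAP 7.4 scores Procedural Success more leniently than Protocol 5.2, Appendix I and SAP 3.0: it stops counting complications at catheterization-laboratory exit and loosens the minor-embolization exception, and the intended window is unclear.

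*SAP*

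**What the plan says.** **The analysis definition.** SAP 7.4 requires placement and release of the occluder with closure, and "discharge from the cardiac catheterization laboratory without device-related complications and without procedure-related complications other than minor device embolization". It describes minor embolization as one that can be resolved percutaneously without surgery or damage to nearby structures. It does not say when the retrieval must happen.

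**The endpoint definition.** Protocol 5.2, the definitions in Protocol Appendix I, and SAP 3.0 share one wording: Technical Success, plus "No procedure-related complications except uncomplicated (minor) device embolization". All three then confine the exception to percutaneous retrieval carried out during the procedure. None mentions leaving the laboratory.

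**The time frame.** SAP 7.4 opens with "Descriptive clinical performance endpoints through 45 days (+15 days) follow-up will be summarized". Protocol 5.2 and SAP 3.0 also place their endpoint lists under a 45-day heading, and within those lists only Technical Success is labelled as an at-implant measure. On the other side, Protocol 3.5 says "Performance of the device is demonstrated by procedural and device success at implant".

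**Where later events go.** SAP 7.5 tabulates adverse events through 45 (+15) days and states "Separate summaries will also be provided for device-related AEs and procedure-related AEs". SAP 7.3 covers the composite components up to Day 60.

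**The concern.** Procedural Success is a listed endpoint, and the SAP gives it two definitions: one in section 3.0 that matches the protocol, and a more lenient one in section 7.4 that the programmer will use. A procedure-related complication that shows itself on the ward or after discharge, such as an access-site complication, would be a failure under the unrestricted wording and is a success under SAP 7.4.

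On a common denominator, the laboratory-exit rate can only equal or exceed the rate under the unrestricted wording. A reader of the final table could not tell which definition had been applied. Earlier experience adds to the difficulty. Protocol 3.4 reports "Procedural success was high during limited market release, with 88/92 (96%) procedural success rate through July 2014", and also 96% for device Version 1.3, without stating the window for either. A single laboratory-exit figure therefore cannot be shown to be like-for-like with them.

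**Working it through.** **Step 1. Compare the definitions.**

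| Element | Protocol 5.2, Appendix I, SAP 3.0 | SAP 7.4 |
|---|---|---|
| Procedure-related complications counted until | no limit specific to this endpoint | discharge from the catheterization laboratory |
| Minor-embolization exception | retrieval during the procedure | percutaneous resolution, no timing |
| Overall time frame | 45 days in the headings of 5.2 and SAP 3.0; none in Appendix I | 45 days (+15) in the lead-in, laboratory exit in the definition |

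The two differences interact. While counting stops at laboratory exit, the looser exception changes little, because few embolizations could fall after the procedure and before the subject leaves the room. If the window is lengthened and the SAP 7.4 exception is kept, an embolization found weeks later and retrieved percutaneously would be exempt. Under the Protocol 5.2 wording it would not be. The exception must therefore be corrected before any 45-day line is built.

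**Step 2. Choose denominators.** The documents do not give the ITT size. The available figures are 56 evaluable and at least 63 enrolled (SAP 7.1), and a maximum of 65 enrolled (SAP 2.2).

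- The plan's figures reproduce. With 3 events in 56 (5.4%), the Clopper-Pearson upper 95% limit is 14.87%, below 15%. With 3 in 55 it is 15.12%. Then 56/0.9 = 62.2, rounded up to 63.
- SAP 4.0 counts consented subjects as enrolled, whereas the ITT set also requires eligibility and sheath insertion. So 56 to 65 is an assumed range for N, not a stated one.

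**Step 3. Effect of one subject.** A subject with a first procedure-related complication after laboratory exit changes the rate by 1/N:

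- N = 65: 1/65 = 1.5 points
- N = 63: 1/63 = 1.6 points
- N = 56: 1/56 = 1.8 points

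**Step 4. Illustration.** The earlier 88/92 is 95.7% (exact 95% CI 89.2 to 98.8). Scaling its 4 failures to 63 subjects gives 4/92 × 63 = 2.7, taken as 3. Treating that as a laboratory-exit result is an assumption, because the window of the earlier rate is not stated. The number of later cases is also assumed, from 0 to 3:

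| Later cases | Successes | Rate | Exact 95% CI |
|---|---|---|---|
| 0 | 60/63 | 95.2% | 86.7 to 99.0 |
| 1 | 59/63 | 93.7% | 84.5 to 98.2 |
| 2 | 58/63 | 92.1% | 82.4 to 97.4 |
| 3 | 57/63 | 90.5% | 80.4 to 96.4 |

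The shift from a few cases is small beside the width of the intervals. It is nevertheless a shift in one direction, set by the definition and not by chance.

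**The case against.** The best defence is that SAP 7.4 fills a gap and overrides nothing. The 45-day headings in Protocol 5.2 and SAP 3.0 also cover Technical Success, which is explicitly an at-implant measure, so those headings cannot fix the window of each endpoint. Protocol 3.5 gives the 45 days the job of capturing procedural safety events and ties procedural success to implant. The in-procedure limit on the embolization exception also fits a peri-procedural endpoint. This stands in part. It rules out saying that the protocol plainly intends a 45-day Procedural Success which the SAP cuts short. It does not supply the laboratory-exit rule, which no protocol section states, and it does not explain why SAP 7.4 leaves out the in-procedure limit.

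A reader might also infer a later window from Protocol 8.1: "In general, any event that occurs within 30 days is considered related to the procedure, unless clear signs are available that they are not". That sentence is a rule for attributing adverse events. It does not say when a success endpoint closes, and it should not be used to settle the window.

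It is also fair to say that no safety information is lost. Late complications reach the SAP 7.5 tables, and composite components reach the SAP 7.3 analysis. That stands, and it is why the point concerns one performance rate and not safety capture.

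Finally, the Protocol 1.0 summary and section 6.10 call for a 45-day TEE, yet SAP 7.4 names no 45-day closure rate, and a reader might call that a dropped endpoint. The documents do not support this. Closure at 45 days is not in the Protocol 5.2 list, and Protocol 13.2 promises other collected data only in general terms.

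**Conclusion.** The point holds as a minor inconsistency. SAP 7.4 departs from Protocol 5.2, Appendix I and SAP 3.0 in two respects, the laboratory-exit cut-off and the missing in-procedure limit on the exception, and it also conflicts with its own lead-in. Which window was intended cannot be determined from the documents.

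The only firm size is 1/N per affected subject, or 1.5 to 1.8 points if N lies between 65 and 56. How many subjects would be affected is unknown and may be none. All these endpoints are descriptive, so no error rate, sample size or safety conclusion depends on the point.

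**What to change.** In SAP 7.4:

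1. Reconcile the lead-in and the Procedural Success definition with Protocol 3.5, Protocol 5.2, Appendix I and SAP 3.0, and state the window explicitly.
2. Restore the in-procedure limit on the minor-embolization exception.
3. Report Procedural Success on two labelled lines, each with an exact 95% CI: to laboratory exit, and through the 45-day (+15) window. In the second line extend only the procedure-related-complication element. Keep the Technical Success elements (leak and device-related complications) at implant, so that a device finding at 45 days does not enter by a side route.
4. Use the same denominator for both lines and state how many subjects lack 45-day follow-up, since SAP 6.3 analyses observed cases without imputation.

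Optional, and not the correction of an error: add a descriptive 45-day LAA closure rate on the Appendix I definition, with an exact 95% CI and the number of missing TEEs. If it is set beside the earlier 100% in Protocol 3.4, note that the earlier figure used residual gap and Appendix I uses residual flow.

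The cost is SAP wording and a few table rows from adverse event data and a TEE already scheduled. Sample size is unchanged. The downside for the sponsor is that the second line may be lower than the first.

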#### 7.5 Other Safety Analysis - Adverse events (AEs)

Site reported adverse events (AEs) during the study will be coded using the Medical Dictionary for Regulatory Activities (MedDRA). The number and percentage of subjects reporting adverse events will be summarized by MedDRA system organ class and preferred term for both ITT and As-Treated analysis sets. Separate summaries will also be provided for device-related AEs and procedure-related AEs. All serious adverse events (SAEs), device-related SAEs, and procedure-related SAEs will also be summarized by system organ class and preferred term. All adverse events occurring through the 45-day (+15 days) follow-up will be summarized.

#### 7.6 Procedural Results

The following characteristics of implant procedure, which are not study endpoints, will be summarized descriptively (n, mean, standard deviation, median, minimum, maximum, and 95% confidence interval, as appropriate) based on the As-Treated analysis set:

- Device deployment duration, defined as the difference in minutes between time of removal of delivery sheath and time of transseptal puncture,
- Procedural duration, defined as the difference in minutes between time of removal of delivery sheath and time of venous puncture,
- Catheterization lab duration, defined as the difference in minutes between time patient left catheterization lab and time patient arrived in catheterization lab,
- Anesthesia type, and

- Contrast volume

#### 7.7 **Protocol Deviations**

All protocol deviations, including rationale for deviation, recorded during the study will be classified by the Sponsor as minor or major and will be listed.
